SYNOPSIS – PROTOCOL REGOBONE

A) CLINICAL TRIAL IDENTIFICATION	
SPONSOR - PROTOCOL CODE NUMBER: UC-0150/1309 EUDRACT N°: 2013-003910-42 VERSION & DATE: VERSION 8.0 – 27/06/2019	
TRIAL TITLE: - A Randomized Phase II, placebo-controlled , multicenter study evaluating efficacy and safety of regorafenib in patients with metastatic bone sarcomas	
ABBREVIATED TITLE: REGOBONE	
PRINCIPAL INVESTIGATOR: [name] La Timone University Hospital, [name] Phone: [name] Fax: [name] e-mail: [contact]	
STATISTICIAN: [name] Centre Léon Bérard [name] Phone: [name] Fax: [name] e-mail: [contact]	
PLANNED NUMBER OF INVESTIGATIONAL SITES: APPROXIMATELY 20 SITES	NUMBER OF PATIENTS: 159

B) SPONSOR IDENTIFICATION
NAME OF THE INSTITUTION: UNICANCER
CONTACT PERSON: [name] Adresse: [name] Phone: [name]. Fax: [name] e-mail: [contact]

C) TRIAL GENERAL INFORMATION
INDICATION: Metastatic bone sarcomas: conventional high grade osteosarcoma, Ewing sarcoma of bone, chondrosarcomas and chordomas and either bone or soft tissue metastatic CIC-rearranged sarcomas
METHODOLOGY: Randomized, placebo-controlled, multicentric, phase II study -This is a double-blind placebo-controlled trial , with 5 cohorts: Cohort A: Osteosarcoma Cohort B: Ewing sarcoma Cohort C: Chondrosarcoma Cohort D : Chordoma Cohort E : CIC-rearranged sarcoma

Cohorts A, B and C will involve a total of **36 evaluable patients each (24 Regorafenib + 12 placebo)**, cohort D will involve a total of **24 evaluable patients (16 Regorafenib + 8 placebo)** and cohort E will involve a total of **27 evaluable patients (18 Regorafenib + 9 placebo)**.

159 patients who meet the eligibility criteria will be randomly assigned in a 2:1 ratio to the following treatment groups :

The Arm A:

Regorafenib (160 mg/d or 120 mg/d) once daily for the 3 weeks on / 1 week off plus Best Supportive Care (BSC) until progression (according to RECIST 1.1), intolerance or withdrawal of consent .

Patients receiving regorafenib who experience disease progression and for whom in the investigator opinion, treatment with regorafenib is still providing clinical benefit, may continue the treatment following consultation with the study coordinator and the sponsor.

The Arm B:

Placebo plus BCS until progression (according to RECIST V1.1) intolerance or withdrawal of consent. Patients who have received placebo will receive open-label regorafenib after objective tumour progression has been documented.

Patients will be stratified at randomization according to histology.

PRIMARY OBJECTIVE:

The principal objective of the trial is to investigate the antitumour activity of regorafenib according to RECIST 1.1 criteria based on central radiological review.

SECONDARY OBJECTIVES:

To evaluate:

1. The progression free survival (PFS) according to RECIST 1.1 criteria
2. Objective response rate [defined as complete response (CR) or partial response (PR) according to RECIST V 1.1 for all cohorts, and CHOI criteria for chordomas] .
3. Overall survival (defined as the time from the date of randomization to the date of death due to any cause).
4. Duration of response.
5. Disease control rate at 6 months is defined as the proportion of patients who have a best response rating of CR, PR or stable disease [SD] according to RECIST guidelines 1.1. SD should be at least 8 weeks.
6. Progression-free rates at 3 and 6 months (PFR-3 and PFR-6), time to progression.
7. Treatment safety will be assessed using the NCI CTC-AE version 4.0 .
8. Growth Modulation Index (GMI).
9. Identification and characterization of biomarkers
10. Time to progression (measured from date of randomization until the date of first observation of progression)
11. Pain assessment for chordomas
12. Progression Free Survival according to CHOI criteria for chordomas

C) TRIAL GENERAL INFORMATION (...)

INCLUSION CRITERIA:

1. Patients must have a histologically confirmed diagnosis of bone sarcoma (osteosarcoma, Ewing sarcoma of bone, chondrosarcoma or chordoma [adults patients only for chordomas]) or CIC-rearranged sarcoma (either bone or soft tissue) with available Formalin Fixed Paraffin Embedded (FFPE) blocks obtained for centralized review;
For CIC-rearranged sarcoma, diagnosis must be confirmed by molecular analysis.
2. Patients with confirmed disease progression at study entry. The “baseline” radiological evaluation should demonstrate disease progression by RECIST V 1.1 for all cohorts (and CHOI criteria especially for chordoma) when compared to a prior disease assessment done

within a prior period of 3 month for osteosarcomas, Ewing sarcomas and CIC-rearranged sarcomas and within 6 months period for chondrosarcomas and chordomas prior to screening
 Note: radiographic progression of disease will be based on at least 2 sets of scans (either MRI or CT) in the 3-month (for osteosarcomas, Ewing sarcomas and CIC-rearranged sarcomas) or 6-month period (for chondrosarcomas and chordomas) prior to or during screening in which radiographic progression of disease, as defined by RECIST for all cohorts (and CHOI criteria especially for chordoma), is demonstrated. No central review of scans (either MRIs or CTs) will be required for study eligibility; these scans must be sent for central review within 10 days after randomization;

3. Metastatic disease (and/or locally advanced disease for chondrosarcomas, CIC rearranged sarcomas, and chordomas) not amenable to surgical resection or radiation with curative intent;
4. Patients must have measurable disease (outside any previous irradiated field) defined as at least one unidimensionally lesion that can be accurately measured as ≥ 10 mm with CT scan according to RECIST V1.1 for all cohorts, and CHOI criteria especially for chordoma. Locally advanced chordomas, with no distant metastasis, can be included, only if MRI is done as the reference imaging exam in order to measure the disease according to RECIST 1.1 criteria.
5. Prior treatment :
 at least one, but no more than two prior (combination) chemotherapy regimen for metastatic disease (or locally advanced disease if applicable) for osteosarcoma, chondrosarcoma and Ewing sarcoma; at least one but no more than three prior chemotherapy regimen for metastatic disease or locally advanced for CIC-rearranged sarcoma; neo-adjuvant /maintenance therapy are not counted towards this requirement. Chordoma not pretreated or with 1 or 2 prior (combination) chemotherapy regimen or with one or two prior molecularly targeted therapy, but no more than 2 prior lines of treatment (whatever the indication) can be included;. At least 4 weeks since last chemotherapy (6 weeks in case of nitrosoureas and mitomycin C), immunotherapy or any other pharmacological treatment and/or radiotherapy;
6. Age ≥ 10 years for osteosarcomas, Ewing sarcomas, chondrosarcomas and CIC-rearranged sarcomas (for chordomas, patients must be ≥ 18 years);
7. Body Surface Area ≥ 1.30 m²
8. Life expectancy of greater than 3 months;
9. ECOG performance status < 2 (Karnofsky $\geq 60\%$) for adults patients;
10. Karnofsky scale $\geq 60\%$ for children aged > 12 years old / Lansky scale $\geq 60\%$ for children aged ≤ 12 years old
11. Patients must have adequate bone marrow, renal, and hepatic function, as evidenced by the following within 7 days of study treatment initiation : normal organ function as defined below :
 - a. Absolute neutrophil count ≥ 1.5 Giga/L
 - b. Platelets ≥ 100 Giga/L
 - c. Hemoglobin ≥ 9 g/dL
 - d. Serum creatinin ≤ 1.5 x ULN
 - e. Glomerular filtration rate (GFR) ≥ 30 ml/min/1.73m² according to the modified Diet in Renal Disease (MDRD) abbreviated formula
 - f. AST and ALT ≤ 2.5 x ULN (≤ 5.0 x ULN for patients with liver involvement of their cancer
 - g. Bilirubin ≤ 1.5 X ULN
 - h. Alkaline phosphatase ≤ 2.5 x ULN (≤ 5 x ULN in patient with liver involvement of their cancer). If Alkaline phosphatase > 2.5 ULN, hepatic isoenzymes 5-nucleotidase or GGT tests must be performed; hepatic isoenzymes 5-nucleotidase must be within the normal range and/or GGT < 1.5 x ULN
 - i. lipase ≤ 1.5 x ULN.
 - j. Spot urine must not show ≥ 1 "+"protein in urine or the patient will require a repeat urine analysis. If repeat urinalysis shows 1 "+" protein or more, a 24-hour urine collection will be required and must show total protein excretion < 1000 mg/24 hours
12. INR/PTT ≤ 1.5 x ULN;
 Patients who are therapeutically treated with an agent such as warfarin or heparin will be allowed to participate provided that no prior evidence of underlying abnormality in coagulation

parameters exists. Close monitoring of at least weekly evaluations will be performed until INR/PTT is stable based on a measurement that is pre-dose as defined by the local standard of care;

13. Recovery to National Cancer Institute-Common Terminology Criteria for Adverse Events (NCI-CTCAE) v4.0 Grade 0 or 1 level or recovery to baseline preceding the prior treatment from any previous drug/procedure related toxicity (except alopecia, anemia, and hypothyroidism);
14. Women of childbearing potential and male patients must agree to use adequate contraception for the duration of study participation and up to 3 months following completion of therapy;
15. Women of childbearing potential must have a negative serum β -HCG pregnancy test within 7 days prior randomization and/or urine pregnancy test within 48 hours before the first administration of the study treatment;
16. Signed informed consent form by adult patients and/or patients parents/legal representatives (if age < 18 years) and age appropriate assent form by the patients' parents/legal representatives obtained before any study specific procedure is conducted
17. Patients must be willing and able to comply with scheduled visits, treatment plan, laboratory tests and other study procedures;
18. Patients or parents/legal representatives affiliated to the Social Security System.

NON-INCLUSION CRITERIA:

1. Prior treatment with any VEGFR inhibitor (thus, any prior exposure to sunitinib, sorafenib, pazopanib, bevacizumab, or other VEGFR inhibitor would render the patient ineligible for this study);
2. Soft tissue sarcomas (including Ewing soft tissue sarcomas) except for CIC-rearranged sarcoma patients;
3. Other cancer (different histology) within 5 years prior to randomization;
4. Major surgical procedure, open biopsy, significant trauma, within the last 28 days before randomization;
5. Cardiovascular dysfunction:
 - Left ventricular ejection fraction (LVEF) < 50%
 - Congestive heart failure (New York Heart Association [NYHA]) \geq 2
 - Myocardial infarction < 6 months before study
 - Cardiac arrhythmias requiring therapy (beta blockers or digoxin are permitted)
 - Uncontrolled hypertension (systolic blood pressure (SBP) > 150mmHg or diastolic blood pressure (DBP) > 90mmHg despite optimal treatment or for children/adolescents SBP and/or DBP > 95th percentile + 5 mmHg)
 - Unstable (angina symptoms at rest) or new-onset angina (begun within the last 3 months)
6. Arterial or venous thrombotic or embolic events such as cerebrovascular accident (including transient ischemic attacks), deep vein thrombosis, or pulmonary embolism within the last 6 months before randomization;
7. Severe hepatic impairment (Child-Pugh C);
8. Ongoing infection > Grade 2 according to NCI-CTCAE v4.0;
9. Known history of human immunodeficiency virus (HIV) infection;
10. Active hepatitis B or C or chronic hepatitis B or C requiring treatment with antiviral therapy ;
11. Difficulties with swallowing study tablets;
12. Prior anticancer therapy, including radiotherapy, endocrine therapy, immunotherapy, chemotherapy (CT) within the last 4 weeks (6 weeks for nitrosoureas and mitomycin C), or other investigational agents ; Concomitant analgesic palliative radiotherapy allowed;
13. Concurrent enrolment in another clinical trial in which investigational therapies are administered;
14. Known hypersensitivity to the active substance or to any of the excipients;
15. Pregnant women, women who are likely to become pregnant or are breast-feeding;
16. For adult patients, individual deprived of liberty or placed under the authority of a tutor;

17. Patients with any psychological, familial, sociological or geographical condition potentially hampering compliance with the study protocol and follow-up schedule; those conditions should be discussed with the patient before registration in the trial;
18. Patients with history of non compliance to medical regimens or unwilling or unable to comply with the protocol.
19. Interstitial lung disease with ongoing signs and symptoms at the time of informed consent
20. Non-healing wound, non-healing ulcer, or non-healing bone fracture
21. Patients with evidence or history of any bleeding diathesis, irrespective of severity
22. Any hemorrhage or bleeding event \geq CTCAE Grade 3 within 4 weeks prior to the start of study medication
23. Use of biological response modifiers, such as granulocyte colony stimulating factor (G-CSF), within 3 weeks of study entry.

EVALUATION

PRIMARY CRITERIA:

The primary efficacy endpoint is the non-progression rate at 8 weeks for osteosarcoma, Ewing sarcoma and CIC-rearranged sarcoma patients, at 12 weeks for chondrosarcoma patients and at 6 months for chordoma patients.

The non-progression rate will be defined as the proportion of patients without disease progression at the defined timepoint after confirmation by central radiological review (using RECIST 1.1).

SECONDARY CRITERIA:

1. Progression-Free Survival [defined using RECIST 1.1] will be measured from the date of randomization until the date of radiological progression or death whatever the cause (if death occurs before progression).
2. Objective response rate [defined as complete response (CR) or partial response (PR) according to RECIST 2009, version 1.1, for all cohorts, and Choi criteria for chordoma] ;
3. Disease control rate at 6 months (defined as the proportion of patients who a best response rating of CR, PR or stable disease [SD]), SD should be at least 8 weeks ;
4. Overall survival (defined as the time from the date of randomization until the date of death due to any cause); if the patients is alive at the date of data base cut off then he will be censored at the data base cut off date;
5. Duration of response (defined as the time from date of first documented objective response of CR or PR, whichever is noted earlier, to first disease progression or death before progression ;
6. Progression-free rate at 3 and 6 months (PFR-3 and PFR-6), defined as the proportion of patients without progression at 3 and 6 months post randomization;
7. Time to progression (measured from date of randomization until the date of first observation of progression);
8. Growth Modulation Index (GMI) defined as ratio of time to PD under regorafenib to TTP under previous treatment. The GMI will be explored in patients receiving regorafenib after randomization;
9. Identification and characterization of biomarkers
10. Toxicity according to NCI-CTC V4.0
11. Pain assessment for chordomas
11. Progression Free Survival according to Choi criteria for chordomas

All efficacy assessments using Choi criteria (only for chordomas) will be performed by central radiological reviewers.

D) DESCRIPTION OF INVESTIGATIONAL MEDICINAL PRODUCTS				
DRUGS:				
Drug Name (IDN)	Commercial Name	Pharmaceutical Form	Route of Administration	Posology
Regorafenib		40 mg tablets	Per os	
≥ 18 years old: 160 mg daily for 3 weeks / 1 week off
 
< 18 years old: 120 or 160 mg daily for 3 weeks / 1 week off according to BSA


THERAPEUTIC SCHEME:
 
 - This is a French multicentre randomized phase II study, and patients will be recruited in around 20 French centers. - Unicancer in France will serve as regulatory sponsor and will perform the monitoring, data management and analyses - This is a double-blind placebo-controlled trial, with 5 cohorts: 
 Cohort A: Osteosarcomas Cohort B: Ewing sarcomas Cohort C: Chondrosarcomas Cohort D: Chordomas Cohort E: CIC-rearranged sarcoma 
159 patients who meet the eligibility criteria will be randomly assigned in a 2 : 1 ratio to the following treatment groups :
 
The Arm A:
 
For adult patients (≥ 18 years old), regorafenib (without exceeding 160 mg/d) once daily for the 3 weeks on / 1 week off plus Best Supportive Care (BSC) until progression (according to RECIST 1.1), intolerance or withdrawal of consent. If the treatment provides clinical benefit to the patient despite radiological progression, he may continue regorafenib following consultation with the coordinator and sponsor.
 
For children Age ≥ 10 years to < 18 years old and BSA ≥ 1.30 m², regorafenib (82 mg/m²) once daily for the 3 weeks on/1 week off (without exceeding 160mg/day) plus Best Supportive care (BSC) until progression (according to RECIST 1.1), intolerance or withdrawal of consent. If the treatment provides clinical benefit to the patient despite radiological progression, they may continue regorafenib following consultation with the study coordinator and sponsor.
 
The Arm B:
 
Placebo plus BSC until progression (according to RECIST 1.1) or unacceptable toxicity. Patients who have received placebo will receive open-label regorafenib after objective tumour progression has been documented.
 
Patients will be stratified at randomization according to histology.
 
TREATMENT DURATION: until progression confirmed by central review and investigator decision or unacceptable toxicity
				

E) STATISTICAL ANALYSIS

SAMPLE SIZE:

The number of patients to include has been calculated for the experimental arm only using a A'Hern's [A'Hern 2001] single-stage procedure for phase II trials (Similar to a Fleming phase II design [Fleming, 1982] but assuming an exact Binomial distribution). Then, the half number of patients has been added to form the placebo arm depending on the randomization ratio 2:1.

Using hypotheses similar to those described above, the number of patients has been calculated as follows:

π is the true probability of success (non progressive patients at **8 weeks** under regorafenib treatment for osteosarcoma and Ewing sarcoma ; at **12 weeks** for chondrosarcoma):

- $\pi_0 = 0.40$ non progressive patients at 8 weeks (0.5 non progressive patients at 12 weeks for chondrosarcoma): the largest non progression proportion which, if true, would clearly imply that the Regorafenib does not warrant further investigation.
- $\pi_1 = 0.67$ non progressive patients at 8 weeks (0.75 non progressive patients at 12 weeks for chondrosarcoma): the smallest non progression proportion that would imply that Regorafenib warrants further investigation.

Assuming a type I error alpha of 0.05 and 80% power, the number of patients required in the experimental arm is 23 patients to reject the null hypothesis $H_0: \pi \leq \pi_0$ versus the alternative hypothesis $H_1: \pi \geq \pi_1$ in a one-sided situation. At the end of the study, Regorafenib will be considered as interesting for further investigation if at least 14 patients are non progressive after 8 weeks of treatment in the experimental arm (for osteosarcoma and Ewing sarcomas) and if at least 16 patients are non progressive after 12 weeks of treatment in the experimental arm for chondrosarcomas.

No formal comparison between the experimental arm and the control arm will be performed.

The placebo arm will only be used to strengthen the results obtained in the experimental arm (randomization avoids patient selection biases). Hence, more patients will be included in the experimental arm, using a 2:1 randomization ratio. Therefore each cohort will involve a total of **36 evaluable patients (24 + 12)**.

Using a similar design as for the other cohorts, the sample size for **chordomas** cohort has been calculated as follows:

π is the true probability of success (non progressive patient at **6 months** under regorafenib treatment):

- $\pi_0 = 0.40$ non progressive patients at 6 months : the largest non progression proportion which, if true, would clearly imply that the Regorafenib does not warrant further investigation. This hypothesis is based on Stacchiotti S *et al* 2012 work showing 6 month PFS rate = 50% ; IC95% (28.8 – 71.1)
- $\pi_1 = 0.75$ non progressive patients at 6 months : the smallest non progression proportion that would imply that Regorafenib warrants further investigation. This hypothesis is supported by Bompas E *et al*. Ann Oncol 2015 showing 6 month PFS rate = 85.3% ; IC95% (60.7 – 95.1)

Assuming a type I error alpha of 0.05 and 80% power, the number of patients required in the experimental arm is 16 patients to reject the null hypothesis $H_0: \pi \leq \pi_0$ versus the alternative hypothesis $H_1: \pi \geq \pi_1$ in a one-sided situation.

At the end of the study, Regorafenib will be considered as interesting for further investigation if at least 10 patients are non progressive after 6 months of treatment in the experimental arm.

As for other cohorts, No formal comparison between the experimental arm and the control arm will be performed. The placebo arm will only be used to strengthen the results obtained in the experimental arm (randomization avoids patient selection biases). Hence, more patients will be included in the experimental arm, using a 2:1 randomization ratio.

Therefore chordoma cohort will involve a total of **24 evaluable patients (16+8)**.

Using a similar design as for the other cohorts and using the results of Regobone osteosarcoma cohort (Duffaud et al. Lancet oncol 2019) showing that median PFS on placebo was 4 weeks for osteosarcoma patients, the sample size **for CIC-rearranged** cohort has been calculated as follows: π is the true probability of success (non progressive patient at **8 weeks** under regorafenib treatment for CIC -rearranged sarcomas):

- $\pi_0 = 0.25$ non progressive patients at 8 weeks (like median PFS of 4 weeks): the largest non progression proportion which, if true, would clearly imply that the Regorafenib does not warrant further investigation.
- $\pi_1 = 0.55$ non progressive patients at 8 weeks (like median PFS of 9 weeks): the smallest non progression proportion that would imply that Regorafenib warrants further investigation.

Assuming a type I error alpha of 0.05 and 80% power, the number of patients required in the experimental arm is 18 patients to reject the null hypothesis $H_0: \pi \leq \pi_0$ versus the alternative hypothesis $H_1: \pi \geq \pi_1$ in a one-sided situation.

At the end of the study, Regorafenib will be considered as interesting for further investigation if at least 8 patients are non progressive after 8 weeks of treatment in the experimental arm.

No formal comparison between the experimental arm and the control arm will be performed. The placebo arm will only be used to strengthen the results obtained in the experimental arm (randomization avoids patient selection biases).

Hence, more patients will be included in the experimental arm, using a 2:1 randomization ratio. Therefore, **CIC-rearranged** cohort will involve a total of **27 evaluable patients (18+9)**.

F) TRIAL DURATION

INCLUSION PERIOD: Approximately 96 months (8 years)

TREATMENT PERIOD: until progression confirmed by central review or unacceptable toxicity: 6 Months (estimate)

Follow-up period: 18 months

OVERALL TRIAL DURATION: Approximately 10 years

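### The 159 patients are both the number randomised and the number evaluable, and each fixed go count meets the stated alpha and power at one regorafenib-arm size that is not the planned one

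*Protocol*

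**What the plan says.** All references are to the protocol synopsis.

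- **Total.** Section A gives "NUMBER OF PATIENTS: 159". Section C (Methodology) says "159 patients who meet the eligibility criteria will be randomly assigned in a 2:1 ratio", and the therapeutic scheme in section D repeats this.
- **Evaluable targets.** Section C (Methodology) sets cohorts A, B and C at "36 evaluable patients each (24 Regorafenib + 12 placebo"), cohort D at "24 evaluable patients (16 Regorafenib + 8 placebo") and cohort E at "27 evaluable patients (18 Regorafenib + 9 placebo").
- **Design.** Section E uses A'Hern's exact single-stage method on the regorafenib arm only, one-sided alpha 0.05 and 80% power. The required regorafenib numbers are 23 (A, B, C), 16 (D) and 18 (E). For A to C the planned size is then "36 evaluable patients (24 + 12"), one more than required.
- **Go rules.** These are fixed counts. Osteosarcoma and Ewing sarcoma succeed "if at least 14 patients are non progressive after 8 weeks of treatment in the experimental arm". The counts for chondrosarcoma, chordoma and CIC-rearranged sarcoma are 16, 10 and 8. Nothing in section E adapts a count to a different number of patients.
- **No other test.** Section E excludes a formal comparison with placebo, so the count is each cohort's only formal decision rule.

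**The concern.** A target expressed in evaluable patients implies that some randomised patients may not qualify. When the evaluable targets add up to exactly the number randomised, that loss is budgeted at zero. This matters because a fixed count is sensitive to the number of patients behind it: a larger arm reaches the count more easily, which raises the false-positive risk, and a smaller arm reaches it less often, which costs power. With arms of 16 to 24 patients, one patient either way can break a stated target. At stake is whether the alpha of 0.05 and power of 80% in section E describe the rule that will be applied.

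**Working it through.** **Inputs (protocol, sections C and E).** Null and target non-progression rates: A/B 0.40 and 0.67; C 0.50 and 0.75; D 0.40 and 0.75; E 0.25 and 0.55. Go counts r: 14, 16, 10, 8. Planned regorafenib arms: 24, 24, 16, 18.

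**Step 1, totals.** Evaluable: 3 x 36 + 24 + 27 = 159. Regorafenib: 3 x 24 + 16 + 18 = 106. Placebo: 3 x 12 + 8 + 9 = 53. 106 + 53 = 159, the number to be randomised.

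**Step 2, reproducing the plan.** With X ~ Binomial(n, p), alpha = P(X >= r | p0) and power = P(X >= r | p1). The smallest n with alpha <= 0.05 and power >= 0.80 is:

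- A/B: 14/23, alpha 0.035, power 0.803
- C: 16/23, alpha 0.047, power 0.804
- D: 10/15, alpha 0.034, power 0.852
- E: 8/17, alpha 0.040, power 0.817

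The stated 23 is reproduced exactly for A to C. For D and E the search gives 15 and 17, one fewer than the stated 16 and 18, with the same counts of 10 and 8.

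**Step 3, the printed counts at neighbouring arm sizes** (alpha / power):

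| Cohort, rule | Planned n | One fewer | Two fewer |
|---|---|---|---|
| A/B, >= 14 | 24: 0.054 / 0.868 | 23: 0.035 / 0.803 | 22: 0.022 / 0.719 |
| C, >= 16 | 24: 0.076 / 0.879 | 23: 0.047 / 0.804 | 22: 0.026 / 0.699 |
| D, >= 10 | 16: 0.058 / 0.920 | 15: 0.034 / 0.852 | 14: 0.018 / 0.742 |
| E, >= 8 | 18: 0.057 / 0.872 | 17: 0.040 / 0.817 | 16: 0.027 / 0.744 |

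Only the middle column meets both targets. Since alpha rises and power falls steadily as n moves away in either direction, no other n does.

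**Step 4, cut-offs that keep alpha <= 0.05 at the planned n:**

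- A/B: 15/24, alpha 0.022, power 0.757
- C: 17/24, alpha 0.032, power 0.766
- D: 11/16, alpha 0.019, power 0.810
- E: 9/18, alpha 0.019, power 0.747

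**Step 5, effect of unassessable patients.** The document gives no rate, so 5% is an assumption. If such patients stay in the denominator as failures, the success rate becomes p1 x 0.95, that is 0.6365, 0.7125, 0.7125 and 0.5225. Power is then 0.64, 0.62, 0.70 and 0.67 with the step 4 cut-offs, and 0.78, 0.77, 0.85 and 0.82 with the printed counts.

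**The case against.** The strongest defence is that each count follows directly after a required number. In cohorts A to C that number is 23, where 14 and 16 work exactly, and the 24th patient can be seen as a spare. This stands in part: the counts are not arbitrary, and losing exactly one regorafenib patient leaves every cohort within both targets. But the planned arm is 24, and nothing says that the rule applies to 23 of the 24. In D and E the required and planned numbers coincide at 16 and 18, where alpha exceeds 0.05. Reading the rule as more than the count would give 11/16, which works, but 9/18 has power 0.747, and the text says at least.

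It is also fair that the excess in alpha is small in A/B, D and E, that A'Hern designs move in whole patients, and that the definition of evaluable and any replacement rule may be in the SAP. Their absence here is not held against the plan.

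Some stronger readings are tempting but unsupported:

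- *The design holds if everyone is evaluable.* It does not: that is where alpha fails in every cohort.
- *The same data could give go or no-go depending on who is called evaluable.* Under a fixed count, dropping a patient with no assessment and scoring that patient as a failure leave the same number of successes, so the same decision. Only excluding an assessed success could change it, and the protocol provides for no such exclusion.
- *Central review will remove patients.* For entry scans the protocol says only that "these scans must be sent for central review within 10 days after randomization", and the same note says central review is not needed for eligibility. Nor does it say that a discordant pathology review makes a patient non-evaluable. Loss is plausible, but these routes are inferred.
- *Replacement cannot restore the planned split because of the blind.* No replacement procedure is described, so this cannot be judged.

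**Conclusion.** The point holds in this limited form. The same 159 serves as randomised and evaluable total, with a margin of one regorafenib patient in each of A to C and none in D and E. The printed counts fit 23, 23, 15 and 17 regorafenib patients, not the planned 24, 24, 16 and 18. With complete data the false-positive risk is 5.4%, 7.6%, 5.8% and 5.7% instead of at most 5%, with power of 0.87 to 0.92. With two regorafenib patients not evaluable the risk is below 5% but power is 0.70 to 0.74 instead of 0.80. Chondrosarcoma has the largest excess in alpha and the lowest power after two losses.

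The figures use exact binomial tails and the protocol's own rates and counts. They assume that the number analysed does not depend on outcome. How many patients will be unassessable is unknown; the loss of two per arm and the 5% rate are illustrations.

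**What to change.** For each cohort still to be analysed:

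1. State one primary denominator, and replace the fixed count by the exact one-sided binomial cut-off against the null rate at that denominator.
2. If the denominator is all patients randomised to regorafenib, with unassessable patients counted as failures, use 15/24 (B), 17/24 (C), 11/16 (D) and 9/18 (E). Restate power as 0.76, 0.77, 0.81 and 0.75 with all assessable, and give the lower figures under a stated unassessable rate (at 5%, about 0.64, 0.62, 0.70 and 0.67).
3. Alternatively, keep the printed counts and state their true alpha (0.054, 0.076, 0.058, 0.057) and power (0.87, 0.88, 0.92, 0.87) at the planned sizes.
4. Call 159 either randomised or evaluable. Keeping it as the number randomised adds no patients. Calling it evaluable would mean randomising 168 to 177 at an assumed 5% to 10% loss (159/0.95 and 159/0.90, rounded up), and would not by itself correct alpha.

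Cohort A's rule should not be changed after the fact, because section E cites its published results when sizing the CIC cohort. Report only its true operating characteristics: alpha 0.054 and power 0.87 if 24 were analysed, 0.035 and 0.80 if 23 were.

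The cost is wording in the protocol and SAP. The downside is that either the stated power or the stated alpha becomes less favourable: with option 2 only chordoma keeps 80% power, and only with all patients assessable.

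### The go cut-offs of 14 (osteosarcoma, Ewing) and 16 (chondrosarcoma) belong to 23 patients, but 24 evaluable are planned; at 24 the type I error is 5.3% and 7.6%, not at most 5%

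*Protocol*

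**What the plan says.** Protocol, section E (Statistical analysis, Sample size), sizes the experimental arm alone by A'Hern's single-stage procedure, described as similar to Fleming's design "but assuming an exact Binomial distribution". For cohorts A, B and C it fixes the following:

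- **Hypotheses:** null 0.40 against alternative 0.67 at 8 weeks for osteosarcoma and Ewing sarcoma; 0.50 against 0.75 at 12 weeks for chondrosarcoma.
- **Size:** "Assuming a type I error alpha of 0.05 and 80% power, the number of patients required in the experimental arm is 23 patients", tested one-sided.
- **Go rule, osteosarcoma and Ewing sarcoma:** "if at least 14 patients are non progressive after 8 weeks of treatment in the experimental arm".
- **Go rule, chondrosarcoma:** "if at least 16 patients are non progressive after 12 weeks of treatment in the experimental arm for chondrosarcomas".
- **Planned cohort size:** "36 evaluable patients (24 + 12"), that is 24 regorafenib and 12 placebo. Section C (Methodology) gives the same split and also calls these patients evaluable.

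No formal comparison with placebo is planned. Nowhere does the protocol recalculate the cut-offs for 24 or restrict the decision to 23 of the 24.

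**The concern.** Each go rule is an absolute count of successes, not a proportion. If one patient is added and the required count stays the same, the hurdle drops: 14 of 23 is 60.9% and 14 of 24 is 58.3%; 16 of 23 is 69.6% and 16 of 24 is 66.7%. The designs have little room for this, because a minimal exact design sits close to its limits. At 23 patients the chondrosarcoma rule already uses 0.0466 of its 0.05.

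Since no between-arm test is planned, the count is the only formal decision rule of each cohort. If it does not have the error rate stated for it, a cohort can be declared positive on data that do not reject its own null hypothesis at the stated level.

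**Working it through.** **Inputs** (all from protocol section E): p0 = 0.40, p1 = 0.67, cut-off r = 14 for osteosarcoma and Ewing sarcoma; p0 = 0.50, p1 = 0.75, r = 16 for chondrosarcoma; calculated n = 23; planned evaluable n = 24; one-sided alpha 0.05; power 0.80.

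**Formula.** With X ~ Binomial(n, p), alpha = P(X ≥ r | p0) and power = P(X ≥ r | p1). The exact single-stage design is the smallest n for which some r gives alpha ≤ 0.05 and power ≥ 0.80.

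**Step 1: reproduce the protocol's figure.** The search gives n = 23 for both pairs of hypotheses, with the protocol's own cut-offs:

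| Cohort | Rule | Alpha | Power |
|---|---|---|---|
| Osteosarcoma, Ewing | 14/23 | 0.0349 | 0.8034 |
| Chondrosarcoma | 16/23 | 0.0466 | 0.8037 |

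The cut-offs are therefore those of the 23-patient design, and the stated method is confirmed.

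**Step 2: same cut-offs with the planned 24.**

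| Cohort | Rule | Alpha | Power |
|---|---|---|---|
| Osteosarcoma, Ewing | 14/24 | 0.0535 | 0.868 |
| Chondrosarcoma | 16/24 | 0.0758 | 0.879 |

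The increase can be checked by hand. With a 24th patient, a cohort passes if it had already reached r among 23, or if it had r − 1 and the extra patient is a success:

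P(X₂₄ ≥ r) = P(X₂₃ ≥ r) + p0 × P(X₂₃ = r − 1)

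- Osteosarcoma, Ewing: P(X₂₃ = 13 | 0.40) = 0.08135 − 0.03492 = 0.04642 (from unrounded values), so 0.03492 + 0.40 × 0.04642 = 0.0535.
- Chondrosarcoma: P(X₂₃ = 15 | 0.50) = 0.10502 − 0.04657 = 0.05845, so 0.04657 + 0.50 × 0.05845 = 0.0758.

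1/0.0758 is about 13, hence about 1 in 13.

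**Step 3: what a bare pass shows.** The one-sided 95% exact lower bound at the cut-off should lie above p0:

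| Result | Lower bound | Null rate |
|---|---|---|
| 14/23 | 0.417 | 0.40, excluded |
| 14/24 | 0.397 | 0.40, not excluded |
| 16/23 | 0.504 | 0.50, excluded |
| 16/24 | 0.479 | 0.50, not excluded |

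**Step 4: what holds alpha.** At 24 each cut-off must rise by one, and power then falls below 80%. No cut-off at 24 meets both targets. The next sizes above 23 that do are shown in the last two rows.

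| Cohort | Rule | Alpha | Power |
|---|---|---|---|
| Osteosarcoma, Ewing | 15/24 | 0.0217 | 0.757 |
| Chondrosarcoma | 17/24 | 0.0320 | 0.766 |
| Osteosarcoma, Ewing | 15/25 | 0.0344 | 0.831 |
| Chondrosarcoma | 18/26 | 0.0378 | 0.820 |

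**Supporting pattern.** The chordoma and CIC-rearranged cohorts look similar. Their stated cut-offs of 10 and 8 are those of exact designs with 15 and 17 patients. At the stated 16 and 18 they give alpha 0.0583 and 0.0569.

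**The case against.** The strongest reply is that the protocol never says in words that the cut-offs apply to 24. The go rule directly follows the sentence that derives 23, and for 23 every stated figure is right. A statistical analysis plan could name the first 23 evaluable patients as the decision set. This does not settle the matter. The successes are counted in the experimental arm, and that arm is planned at 24. Both places that give the planned size call the patients evaluable, so the 24th cannot be read as a dropout allowance. If 23 was meant, the protocol needs to say which 23, because one patient can decide the result.

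The second reply concerns size. For osteosarcoma and Ewing sarcoma the excess is 0.35 percentage points (0.0535 − 0.05). In a discrete phase II screen that is close to negligible, and it affects only a result of exactly 14 out of 24. The extra patient also raises power to 0.868 and 0.879. This stands for those two cohorts, but it does not carry over to chondrosarcoma, where the excess is 2.6 points.

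Third, raising the cut-offs at 24 exchanges one missed target for another, since power drops to about 76–77%. That is true and should be disclosed with the change. Finally, the placebo arm is meant to support interpretation, so the count is not read in isolation; it remains the only formal rule.

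**Conclusion.** The concern holds. The cut-offs of 14 and 16 have the stated error rates at 23 patients and not at the 24 evaluable patients planned. At 24 the one-sided type I error is 5.3% for osteosarcoma and Ewing sarcoma and 7.6% for chondrosarcoma, against a stated 5%. The text is wrong as written for all three cohorts, but the practical weight lies in chondrosarcoma.

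This rests on three things: the exact binomial, which the protocol names; the protocol's own null and alternative rates; and reading the count as taken over the whole planned arm of 24 evaluable patients. If exactly 23 patients entered the decision, alpha would stay within 5%. That 24 was chosen so the arm divides evenly at 2:1 is an inference (half of 23 is not a whole number), and the result does not depend on it.

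**What to change.** State the cut-off for the number of evaluable regorafenib patients actually analysed: at least 14 (osteosarcoma, Ewing) or 16 (chondrosarcoma) if 23 are evaluable; at least 15 or 17 if 24 are evaluable, with power at 24 restated as 76% and 77%. If the sponsor prefers to keep 14 and 16 with 24 patients, restate the one-sided type I error as 5.3% and 7.6%.

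Two alternatives keep both stated targets. One is to specify in advance that the decision uses the first 23 evaluable regorafenib patients, with the 24th reported descriptively. The other is to re-derive size and cut-off together (15/25 and 18/26), which needs more patients.

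Any change of rule must be made prospectively, for cohorts not yet analysed. The protocol does not give the analysis status of the Ewing and chondrosarcoma cohorts, so this has to be confirmed first. Section E already cites the osteosarcoma results, so for that cohort only the error rate should be restated.

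The cost of the main fix is wording in the protocol and analysis plan, with no added patients. Either stated power falls a few points below 80%, or stated alpha rises above 5%.
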